Webinar /Staff Module: VA-INTERACT Advance Care Planning (ACP) Tools
Webinar /Staff Module: VA-INTERACT Quality Improvement Tools
Webinar /Staff Module: VA-INTERACT Interacting with your Hospital
Webinar /Staff Module: VA-INTERACT sustainability

2.) A 12-18 month monitoring and data collection period to review the results of the intervention following the 6 month training period. In this second phase of the intervention, research staff will continue to host conference calls and participate in more of an observational and advisory role. The research team may host occasional refresher trainings and other web-based modules for new or existing staff interested in participating.

During the 6 month training period, the project Champions, as well as key CLC staff, including certified nursing assistants (CNAs), licensed nursing staff, ancillary staff, therapists, social workers, administrative nurses, the medical director, and medical providers (MDs, NPs, and PAs) will be expected to participate in the online training curriculum. Night and weekend staff will also be expected to complete the curriculum, as many acute care transfers occur at night and on weekends. These types of staff members successfully completed training in community-based trials of INTERACT.

The 6 month training curriculum includes a combination of online resources and teleconference calls facilitated by one or more of the VA-INTERACT research staff. Online resources include eight annotated Power Point presentations with voice over and video clips of case examples to illustrate the rationale and goals for the program and how the INTERACT tools can be incorporated effectively into every day practice, and a post-session feedback assessment. Individual CLC staff will be encouraged to take part in the designated staff modules hosted through the study SharePoint. Staff will be able to anonymously complete the modules and feedback assessment identifying only their job category within the CLC. Completion of individual webinars will be tracked and aggregate level reports generated for facility Champions in order to ensure that key staff members complete the curriculum during the training period. Completion of the modules will be tracked through the project specific SharePoint. Training sessions will not be linked to individual CLC staff.

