Documenting Intervention Fidelity: The process of implementing and remaining true to the fidelity of INTERACT will be documented in a uniform manner across all intervention CLCs using the web based training, documentation of attendance on conference calls, qualitative notes from site visits, and from fielding trouble shooting calls. Specific items of interest that will be examined and reported will include: a change in the Champions; the proportion of staff who complete the web-based training; the number of Stop and Watch Early Warning Tools used; the number of SBAR Progress Notes completed relative to the number of hospitalizations per month; and any increase in the number of CLC residents with advance care directives. Variation between CLCs participating in the INTERACT intervention will be one of the foci of an implementation report. We will also document the association between a global assessment of “adherence” to the INTERACT intervention and the degree of reduction in the actual rate of hospitalization from CLC by CLC Veteran. Counts of contacts, calls and numbers of forms filed will be differentiated between the first 6 month period and the second 12 month monitoring and data collection period.

In order to evaluate intervention fidelity, we will use data on the number of CLC staff who complete INTERACT training, participate on teleconferences, and obtain information from project Champions during regularly scheduled calls on the use of specific INTERACT tools (Stop and Watch Early Warning Tool, SBAR, Quality Improvement Tools, and Advance Care Planning Tracking). The Project Coordinator will track receipt of data and will contact project Champions with reminders and follow-ups if data is not submitted.

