INTERACT VA CLC Version 1.0 tools will be introduced and suggested implementation will be provided. (See Appendix # 2, *INTERACT VA CLC Version 1.0 Tools*) Champions will be asked to engage key personnel in online training modules to assist personnel with implementation and get feedback on use of tools. The online modules will be available through a secured VA website portal for each site to have individual access. Individual employees will remain anonymous, identifying only their position in the CLC when completing the modules and post session quizzes. (Only Providence VAMC Research staff will have access to individual responses. Providence Research staff will quantify the results and share with clinicians so they can provide feedback to sites on their implementation status and evaluate process measures related to uptake of *INTERACT* implementation at a particular CLC (See Appendix # 5 , *INTERACT Webinars & Staff modules*). In between webinars personnel will be asked to use the tools and track acute care transfers and hospitalization rates using existing information systems within the CLC (paper or electronic). Conference calls with each CLC will be held between webinar sessions to assess and support the implementation of *INTERACT* from the Champions and leadership perspective. Cohort conference calls will be held periodically to get feedback across sites on the implementation process and *INTERACT* uptake, as well as an opportunity for sharing successes and challenges.

SBAR usage will be monitored regularly throughout the study timeframe for each CLC. (Appendix # 6, Interview Guide) Beginning after the introduction and use of SBAR (approximately 2 months into the 6 month training period), CLC Champions will review SBARs of all CLC Veterans for whom the form was completed during the timeframe of interest. (These forms are completed by CLC nursing staff when they notice a clinical change in a patients' condition that warrants a discussion with the physician regarding the need for changes in standing orders.)

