The proposed documentation of the implementation of the INTERACT intervention will have both a quantitative as well as a qualitative component. We will rely upon the data recorded as part of the documentation of the intervention process to characterize the extent of adherence to INTERACT over the course of the training period and across the participating CLC sites. Each site will be characterized in terms of the following: percentage of direct care staff who initiated and completed the on-line training; the percentage of training calls attended by the Champions; the proportion of hospitalizations for which a root cause analysis was completed by the nursing staff; and the number of SBAR and Stop & Watch tools reported on by the Champions per week. To document changes in the intervention from the beginning of the training period to the end of the monitoring period, we will calculate some metrics on a monthly basis to share with the CLC, allowing for the likelihood that the level of adherence of the intervention will change over time, presumably rising throughout the 6 month training period and

beginning to decline during the monitoring period.

The qualitative component of the intervention will be undertaken throughout the monitoring period during the numerous regularly scheduled calls with CLC representatives. An audit trail of anecdotal feedback derived during these calls will be kept in a restricted folder on the SharePoint which only Providence Research staff on this project will have access to.

We are aware the data may be impressionistic and may not accurately reflect the variation in how the intervention was implemented over the duration of the project. However, having information on the utility of the INTERACT tools, how they were used in practice, and how that use changed from the start of the active 6 month training period compared to the 12 month monitoring period will be very valuable in ascertaining fidelity to INTERACT protocols and uptake of intervention. This may help explain possible differential results between facilities.

Aim #4: *To test the effect of the INTERACT intervention on the rate of reduction in hospitalizations from intervention CLCs as compared to the matched control CLCs and to determine via a formalized structured implicit review (SIR) process whether the intervention was associated with a reduction in “avoidable” hospitalizations and that it did not lead to negative outcomes like mortality and ADL decline.*

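### The share of staff who completed the online training cannot be derived as worded for the eight-module curriculum, because module records are anonymous and not linked within person

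*Combined protocol and SAP*

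**What the plan says.** Three statements call for a count of people:

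- Aim #3 characterises each site by the "percentage of direct care staff who initiated and completed the on-line training".
- Documenting Intervention Fidelity lists "the proportion of staff who complete the web-based training".
- The same section adds that "we will use data on the number of CLC staff who complete INTERACT training".

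The training is a curriculum of eight modules (Section C, Training). The data to be collected are described as follows:

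- Training: "Staff will be able to anonymously complete the modules and feedback assessment identifying only their job category within the CLC".
- Implementation of INTERACT Training Curriculum: "Individual employees will remain anonymous, identifying only their position in the CLC when completing the modules and post session quizzes".
- Training again: "Training sessions will not be linked to individual CLC staff".

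The Training section also says "Completion of the modules will be tracked through the project specific SharePoint" and "Completion of individual webinars will be tracked and aggregate level reports generated for facility Champions". Each site reaches the modules through its own access, so a completion can be assigned to a CLC. CLC staffing data will be drawn from the Corporate Data Warehouse (Facility Level Data), but for describing staffing levels; they are not named as the denominator for training.

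**The concern.** Finishing a curriculum of eight modules is a property of a person: the same employee has to appear in all eight. The records show how many times each module was completed, by job category and CLC. They do not show whether eight completions came from one person or eight, or whether one person did the same module twice. Refresher sessions and online training for newly hired staff are both planned for the monitoring period, so repeats and turnover are foreseeable. The protocol gives no rule for joining one person's records, removing repeats or choosing the headcount.

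The likely outcome is that completions are divided by some headcount and the result is printed as a percentage of staff trained. That label would claim more than the data support, and repeats could even take the figure above 100%. The measure is meant to characterise fidelity under Aim 3, and the protocol expects the fidelity information to help explain differing results between facilities. It also plans to relate a global assessment of adherence to the fall in hospitalization. If training completion enters that assessment as a person-level percentage, an unidentified quantity becomes an explanatory variable.

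**Working it through.** The protocol states no target or numerical value for this measure, so there is no figure to reproduce. The check is what the unlinked counts can and cannot identify.

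**Inputs.** Number of modules: 8 (Training). Share of staff completing each module: p, taken as equal across modules. The protocol gives no value, so p is an assumption shown over a range. Completion is taken to mean all eight modules; the protocol does not define it.

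**All eight modules.** A share 1 − p misses each module. The share missing at least one is at most 8(1 − p) and at least 1 − p. So the share completing all eight lies between max(0, 1 − 8(1 − p)) = max(0, 8p − 7) and p.

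| Assumed p | 8p − 7 | Share completing all eight |
|---|---|---|
| 80% | −0.60 | 0% to 80% |
| 90% | 0.20 | 20% to 90% |
| 95% | 0.60 | 60% to 95% |
| 99% | 0.92 | 92% to 99% |

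The lower limit stays at zero until 8p = 7, that is p = 87.5%.

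**Initiated.** The share completing at least one module lies between p and min(1, 8p). At p = 80% that is 80% to 100%, so the records bound this part without fixing it.

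**One module at a time.** No link is needed here, only a headcount and few repeats. Suppose 80 records for one module come from a CLC with 100 staff (both assumed). If a share r of the records are repeats, the number of different people is 80(1 − r): 80 at r = 0, 76 at 5%, 72 at 10% and 64 at 20%. The records do not show r.

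So a per-module figure is obtainable, with an error that depends on repeats and on the headcount chosen. The whole-curriculum figure is only bounded, and the bounds are wide unless nearly everyone completes every module.

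**The case against.** - **Completions are tracked.** They can be assigned to module, site and job category, and divided by a headcount. This stands. A reader might infer that no training measure can be obtained, and the documents do not support that.
- **The protocol never says that completion means all eight modules by one person.** This stands too. Read module by module, the bounds do not apply. But wording about staff who initiated and completed the training is naturally read as person-level, and under any reading repeats cannot be removed.
- **The bounds are extremes.** A reader might infer that two CLCs with the same counts would typically differ by 80 points. That gap needs opposite extremes of overlap at an assumed p of 80%: in one CLC every employee misses at least one module, in the other the same people do everything. It is a limit of what the data can say, not an expected error.
- **It is one measure among several.** Aim #3 lists it beside Champions' attendance at training calls, root cause analyses and tool counts, none of which depends on this linkage. The documents do not support calling it the main fidelity measure.
- **Reports by job category still help Champions.** They can show which groups lag, and a category held by one person is in effect individual. But they cannot show that particular people finished the curriculum.
- **Anonymity is deliberate.** It is promised to staff in two places and may well be the right choice. The measure should then be described in terms that anonymity allows.

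**Conclusion.** The measure as worded under Documenting Intervention Fidelity and Aim #3 cannot be derived for the eight-module curriculum. What the design yields is completions per module, CLC and job category, with repeats, refreshers and new hires not separable. On the assumption that completion means all eight modules, the share completing is known only to within 0% to 80% when each module stands at 80%, narrowing to 60% to 95% when each stands at 95%.

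The effect is limited to one Aim 3 fidelity measure and any adherence analysis that uses it. A reader might infer that the main trial result is affected. The primary outcome is the CLC hospitalization rate and does not use this measure. The section on CLC agreement to participate does require some minimum participation in training and allows a poorly engaged site to be dropped with its matched control, but it states no threshold and does not tie the decision to this percentage. An effect on which pairs remain is possible only if module counts inform that decision, which the text does not say.

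**What to change.** Amend Documenting Intervention Fidelity and Aim #3 to:

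1. Report completions per module, by job category and CLC, over a stated staff headcount for the 6-month training period. The planned staffing extract may supply it, if it gives headcounts in matching job categories; this needs checking.
2. State that repeat completions are not removed.
3. Count completions after month 6 separately by date. This assumes that the tracking records carry a date, and it only partly sets apart refreshers and new hires.
4. Not label the result the percentage of staff who completed training, nor enter it under that name in the adherence assessment.

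The cost is a short wording amendment, and no new data collection if a suitable headcount is already in the extract.

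For any training not yet delivered, staff could be offered a self-generated, non-identifying code to enter at every module, so that completions link within person. It would need one added field. The downsides are mistyped codes and somewhat weaker anonymity in small job categories, and because the code is optional, linkage would be incomplete. It cannot recover past records: Figure 5 schedules CLC training for 4/15 to 8/15, and this version is dated 06/28/17. If training ran to that schedule, the rewording is the part that matters.

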CLC agreement to participate: Up to 15 CLCs will be identified as potential participants in the INTERACT intervention program based on a pair matching system and random selection of one CLC from each pair. If the selected CLC does not agree to participate the pair will be dropped and we will go back to the remaining list of potential pair matches and select another site until up to 15 have agreed to participate or we have contacted all eligible sites.

The formal training at each CLC is scheduled to occur over a 6 month period followed by 12-18 additional months of observation. A minimum level of participation in the training is required to

ascertain that the intervention has been embraced by the CLC staff. The Providence research staff will monitor the CLCs' participation in the intervention. If a CLC is doing poorly and the Champions seem to be unable to engage and motivate the staff, we may drop the site or try to recruit an additional Champion(s). This is one of the reasons for matching extra pairs of CLCs. One of the strengths of the pair matched design is that if one of the intervention CLCs is dropped we can readily drop the matched control site without having to worry about unbalancing the design.

Each CLC will follow the procedure below to become an active participating CLC in the INTERACT intervention. Selected CLCs will be contacted with a letter from the PI, [name], Co-PI [name], MPH, INTERACT Developer, [name], and GEC leadership containing introductory material, describing the INTERACT training program being proposed. After the letter, follow up contact will be made with each CLC to determine participation. Sites who agree to participate will be asked to sign a Research Study Agreement (See Appendix # 3, Research Study Agreement).

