Data are de-identified before analytic files are created, providing an additional level of protection. Furthermore, COIN employees have signed an oath of confidentiality, and its violation is sufficient grounds for immediate termination. Finally, analysis results are always presented in aggregate form with minimum cell sizes restricted to greater than 10 in accordance with VHA and CMS Data Use Agreements and policies.

The project will use real time CDW data available from VINCI to provide CLCs with hospitalization rates and mortality data for the selected INTERACT CLCs on a regular basis. The Providence research staff will also track this data for the pair matched facilities and provide aggregate, de-identified data for the Data Safety Monitoring Board.

Data Safety Monitoring Plan:

To ensure the safety of Veterans in the CLC and confirm the intervention is not reducing hospitalizations to the detriment of Veterans' we have created a safety monitoring plan as described below which has been reviewed and signed off on by the Data Safety Monitoring Board (DSMB).

1. We will generate mortality data for all CLC residents in both INTERACT (experimental) and control facilities, charting changes in mortality rates relative to the historical and contemporary mortality rates of paired facilities;
2. The INTERACT (experimental) CLCs will complete SBAR Progress Notes regarding acute changes in conditions for Veterans. These forms are completed by CLC nursing staff when they notice a clinical change in a patients' condition that warrants a discussion with the physician regarding the need for changes in standing orders. There is considerable detail on patients' clinical condition at the time along with information on the disposition of the case;
3. Staff will transfer the names of cases for which an SBAR is completed to Providence VAMC research staff via a joint SharePoint and Providence staff will keep records of SBARs used.
4. The INTERACT (experimental) CLCs, during every other week calls with the site Champions will review the record of all CLC Veteran's for whom an SBAR form was completed during the previous timeframe.

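### Does the undefined global adherence assessment, made by staff who may know the hospitalization rates, need a change to the plan?

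*Combined protocol and SAP*

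**What the plan says.** Documenting Intervention Fidelity announces the analysis: "We will also document the association between a global assessment of" adherence and "the degree of reduction in the actual rate of hospitalization from CLC by CLC Veteran". The same section lists items to report: change of Champion, staff completing the web training, Stop and Watch counts, "the number of SBAR Progress Notes completed relative to the number of hospitalizations per month", and any rise in advance directives. Its next paragraph names the data source: "In order to evaluate intervention fidelity, we will use data on the number of CLC staff who complete INTERACT training", with teleconference participation and tool use reported by the Champions. It also separates counts from the training period and the monitoring period.

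Aim #3 gives an overlapping list: training started and completed, training calls attended, hospitalizations with a root cause analysis, and SBAR and Stop & Watch tools per week. It adds a qualitative log of call feedback "which only Providence Research staff on this project will have access to", and then a caution: "We are aware the data may be impressionistic and may not accurately reflect the variation in how the intervention was implemented".

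On who sees what, Aim #2B says "The Providence research staff will monitor the CLCs' participation in the intervention". Data Assurances says "The project will use real time CDW data available from VINCI to provide CLCs with hospitalization rates and mortality data", and has the Providence research staff track the same data for the matched facilities.

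**The concern.** The assessment has no stated components, weights, period or rater. The group that follows participation and holds the call log also appears to be the group that follows hospitalization rates, and the CLCs whose Champions report tool use receive those rates too. Elsewhere the protocol does guard its judgments: the exit survey is run by staff outside Aim #2B, and the chart reviewers in the Structured Implicit Review are not told whether a chart is from before or after the intervention. The adherence assessment has no such guard.

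The result would be read with interest. The Introduction reports reductions of 24% in homes rated engaged and 6% in homes rated not engaged, a gap of 18 points. The section on impact for the VHA ties the expected 20% reduction to CLCs that fully implement the program. If knowledge of the outcome leaked into the rating, a similar gap could appear with no adherence effect behind it.

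**Working it through.** The documents give no figure for this association, so there is nothing to reproduce. The check has three parts.

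**1. Is a rule missing, or is a rule wrong?** No section combines the fidelity items into one assessment. But no section prescribes a bad combination either. Aim #3 says the extent of adherence will be characterized from data recorded during the intervention, and its quantitative items are counts and percentages. Module completion is tracked through SharePoint and SBAR notes are extracted from VistaWeb. Knowing the outcome cannot easily move such figures. The caution about impressionistic data follows the paragraph on the qualitative component, and nothing says that component forms the global assessment.

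Two items have hospitalizations in the denominator: SBAR notes per hospitalization, and the proportion with a root cause analysis. With SBAR use constant, a 20% fall in hospitalizations raises the first by 1/0.8 = 1.25, or 25%. An analyst would see this and leave it out of a score to be related to the same fall. The plan lists it for reporting and does not put it in the score.

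**2. How large could a false gap be?** Illustration only, with no true adherence effect.

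- Reduction per CLC = 1 − exp(log .83 − SD·z), with z standard normal. The mean reduction is about 17%, as in the earlier evaluation in the Introduction.
- Rating = r·z + √(1 − r²)·a, with a independent standard normal.
- The top 5 of 8 CLCs (or 10 of 15) are called engaged, near the 17 to 8 split in the Introduction. Gap = mean reduction in engaged minus the rest.
- Assumed, not in the documents: r, the between-CLC SD of the log change, and the use of a split at all.

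Mean false gap in percentage points, and share of runs with a gap of 18 or more, for 8 CLCs:

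| SD | r = 0 | r = .2 | r = .35 | r = .5 |
|---|---|---|---|---|
| .10 | 0; 0.2% | 2; 0.6% | 4; 1% | 6; 2% |
| .15 | 0; 3% | 4; 6% | 7; 10% | 9; 16% |
| .30 | 0; 17% | 8; 28% | 14; 40% | 20; 51% |

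With 15 CLCs and SD .15 to .30, the mean gaps are 4 to 8, 7 to 14 and 10 to 21 points for the three non-zero values of r. At SD .10 an 18-point gap occurs in under 1% of runs.

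The SD matters as much as r. Counting noise alone gives √(2/n), with n = residents × 2 years × rate. At the 50-bed minimum with all beds filled:

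- rate 1.3 per person-year: n = 130, SD = .12
- rate .5: n = 50, SD = .20

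With 100 residents these become .09 and .14. The rate of .5 is an assumed alternative, because the 1.3 in Preliminary Studies exceeds the maximum of 1.1 stated beside it.

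**3. What can the association bear?** With r = 0 and 8 CLCs, the 95% range of the gap is −18 to 19 points at SD .15 and −37 to 40 at SD .30. The two-sided 5% critical correlation is t/√(n − 2 + t²). For 8 CLCs it is 2.447/√(6 + 5.988) = .71, and for 15 it is 2.160/√(13 + 4.666) = .51. Even a perfectly masked score could support only a descriptive remark.

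**The case for a change.** The strongest case for a change is that the remedy costs about a page: name the components, the combining rule and the period before linking to outcomes. The plan already accepts the principle of separation for the exit survey and the chart review. The absence is real, and the false gaps above are not trivial if r and the SD are large. The calls also review prevented and actual transfers, so anyone rating from the call log would meet outcome information.

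Part of this stands. The definition is missing, and writing it down would be good practice. But the staff overlap is less plain than it looks. The Management Plan assigns implementation, outcome files and the monthly hospitalization analyses as separate duties. Personnel distinguishes intervention teams from research and data teams. Data Assurances restricts identified data to the system analyst, the programmer and the investigator. None of this is masking: the principal investigator coordinates both sides, the teams hold joint calls, and study facilitators also have access to project data. It does mean that a rater with full sight of the outcome is not a stated feature of the design. Part of the Personnel text was not available, so who makes the assessment cannot be settled from what was read.

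Masked raters would also bring a loss. They would have to work without call notes that discuss transfers, and so give up some of the qualitative detail that Aim #3 is meant to supply.

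**Conclusion.** No change to the plan is called for. The gap is one of detail that analysts can fill sensibly from the training, call-attendance and tool-use counts, reported separately for the training and monitoring periods, as the fidelity section already provides for its counts. No stated rule would give a wrong answer if followed.

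The consequence is bounded. The association is descriptive, within the intervention arm and based on 8 to 15 CLCs. The difference-in-difference comparison of matched pairs under Aim #4 does not use it. A false gap near the 18 points of the earlier evaluation needs both a rating that follows the outcome and a between-CLC SD toward the top of the assumed range. At SD .10 with 8 CLCs it occurs in 0.6% to 2% of runs for r of .2 to .5. These figures rest on assumed values of r and the SD and on an engaged split that the plan does not state. The conclusion would differ if the assessment turned out to be an open judgment made with the rates in view and the report presented the resulting gap as an effect of adherence. The protocol says neither.
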